5.3. Safety Population

The safety population will include all enrolled subjects who receive at least 1 dose of treatment.

The safety population will be used for all analyses of safety endpoints unless specified otherwise and for the summaries of patients in listings related to dosing of study drug.

6. STUDY SUBJECTS

6.1. Disposition of Subjects

The disposition of subjects will be summarized for all subjects screened in the study. The following disposition information will be summarized overall:

- The number of subjects screened.
- The number of subjects who failed screening and the reason for screen failure.

All percentages will use the number of screened subjects as the denominator.

The following disposition information will be summarized for all subjects enrolled.

- The number of subjects enrolled.
- The number and percentage of subjects in the mITT population, PP population, and safety population.
- The number and percentage of subjects who completed the study (through Visit 7)
- The number and percentage of subjects who withdrew from the study and the reason for withdrawal

All percentages will use the number of enrolled subjects as the denominator.

A data listing of subject disposition for all enrolled subjects and a data listing of screen failures will also be provided.

6.2. Demographic and Other Baseline Characteristics

Subject demographics and other baseline characteristics will be summarized descriptively for the safety population for each dose (1.2 g/day, 1.95 g/day, 2.4 g/day) and overall. Summaries by dose classify subjects according to the maximum dose of adrlipase received during the study.

Demographic data will include:

- age
- sex
- race
- ethnicity

Age (years) will be age at screening, as collected on the CRF.

Baseline characteristic data will include:

- gastric acid suppression use at screening
- CFTR (cystic fibrosis transmembrane conductance regulator) modulator use at screening (yes, no)
- name of pre-study PERT

- pre-study PERT dose (lipase units/kg/day)
- weight
- height
- body mass index (BMI)
- years since diagnosis of EPI.

Descriptive statistics (number of subjects, mean, SD, minimum, median, and maximum values) will be presented for continuous variables. For qualitative or categorical variables, the number and percentage of subjects within each category will be presented.

Individual data for demographics, baseline characteristics, and medical history will be presented in the data listings for subjects in the safety population. A data listing of any inclusion/exclusion criteria not met will also be presented for all screened subjects.

Partial missing dates will be imputed for the purposes of determining time since diagnosis of EPI as follows:

- For a partially missing diagnosis date where the day is missing, but the month and year are present, the day will be set to the first day of the month.
- For a partially missing diagnosis date where the day and the month are missing, but the year is present, the month and day will be set to January 1st.

Years since diagnosis of EPI will be calculated in years using the imputed diagnosis date and the date of screening as [(date of screening – diagnosis date)]/365.25, rounded to one decimal place.

6.3. Prior and Concomitant Medications

The prior and concomitant medications will be coded using the latest version of World Health Organization Drug Dictionary (WHODrug) Global Version (2022-SEP) to identify the drug class and preferred drug name.

Concomitant medications will include all medications that started on or after day of first dose of the study treatment or that stopped on or after day of first dose of study treatment. Prior medications will include all medications that started and stopped prior to the day of first dose of the study treatment.

The number and percentage of subjects using prior and concomitant medications will be displayed overall and by maximum dose of adrulipase received during the study and will be tabulated by Anatomical Therapeutic Chemical (ATC) level 1 term, ATC level 2 term, and preferred drug name for all subjects in the safety population. If a subject has more than 1 medication within an ATC level 1 term, the subject will be counted only once in that ATC level 1 term. Similarly, if a subject has more than 1 medication within an ATC level 2 term, the subject will be counted only once in that ATC level 2 term. If a subject has more than 1 medication that codes to the same preferred drug name, the subject will be counted only once for that preferred drug name. All percentages will use the number of subjects in the safety

population as the denominator. The tabular summary will be sorted by descending frequency by ATC level 1 term, ATC level 2 term, and preferred drug name.

Prior and concomitant medication data will also be presented in a data listing for subjects in the safety population.

6.4. Medical History

Medical history will be coded using Medical Dictionary for Regulatory Activities Terminology (MedDRA) version 25.1. Medical history data will be listed for the safety population including the condition, start date, end date and whether the condition is ongoing.

7. STUDY OPERATIONS

7.1. Protocol Deviations

Protocol deviations will be identified on an ongoing basis by the study team.

The number and percentage of subjects with:

- at least 1 protocol deviation;
- at least 1 major protocol deviation;
- at least 1 protocol deviation for each protocol deviation type

will be summarized overall and by maximum dose of adrulipase received during the study for the mITT population.

Line listings will be provided to the study team for the manual classification of major vs. minor protocol deviations and the FirstWave study team will confirm classification of major vs. minor at a data review meeting prior to database lock. Each major deviation will be categorized as either important or not important with respect to the effect on the primary endpoint analysis.

All subjects in the safety population having a protocol deviation and the details for the protocol deviation will be identified in a subject-level data listing. The listings will include the date of the deviation, protocol deviation type, if it was IRB reportable, date reported to IRB, any noted comments, and the deviation corrective and preventative action (CAPA).

7.2. Randomization

Not applicable.

7.3. Measures of Treatment Compliance

Treatment compliance will be summarized in terms of g/day using a compliance rate and will be displayed overall and by maximum dose of adrulipase received during the study.

The compliance rate will be calculated as:

$$[\text{Actual Dose g/day} / \text{Expected Dose g/day}] * 100$$

The actual dose (g/day) a subject received will be calculated as:

$$[(\text{number pills dispensed} - \text{number of pills returned}) * 0.15 \text{ g}] / \text{number of actual study days on adrulipase},$$

where the number of actual study days on adrulipase is calculated as:

$$(\text{date/time of last adrulipase dose} - \text{date/time of first adrulipase dose}) / 86400 + 1.$$

The expected dose for adrulipase depends on whether the subject titrated to a higher dose during the study, e.g. low dose (1.2 g/day), medium dose (1.95 g/day), high dose (2.4 g/day), and is calculated as:

$$1.2 \text{ g}/(\text{days on low dose}) + 1.95 \text{ g}/(\text{days on medium dose}) + 2.4 \text{ g} (\text{days on high dose})$$

First Wave BioPharma, Inc.
{Statistical Analysis Plan - Protocol #} FWB-CF-2.03

Treatment compliance will be summarized using descriptive statistics.

As described in Section [5.2](#), subjects found to be <80% compliant with adrulipase will be excluded from the PP population.

Individual data for study drug (number of capsules) dispensed and returned, and treatment compliance will be listed for subjects in the mITT population. a

Note that since capsules are dispensed at one visit and returned at one visit (e.g. not separately b

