- On Day 16 + 5 days (Part 1) or Day 10 + 3 (Part 2) (Visit 6), patients will undergo admission to a controlled supervised facility for stool collection to support the CFA and CNA assessment and weight. A +5-day (Part 1) or +3-day (Part 2) visit window is allowed to accommodate investigative site staff and patients' schedules for the supervised confinement.
- After appearance of fecal stool dye markers has been measured, patients CFA and CNA will be measured under their dose of adrulipase using standardized high-fat meals during the 3-day standardized diet. Additional detailed information provided in the study operations manual should be followed.
- The CFA calculation will be based on the measured fecal fat content in relation to ingested fat quantities during the 3-day stool collection period.

After completion of the initial treatment period during the completion of V6, patients will be instructed to switch their study medication to their prestudy porcine PERT. The stool collection and dietary procedures will be conducted as described in [Section 9.2.4.1.](#) (Instructions for Supervised Confinement)

The following procedures will be performed at Visit 6:

- Begin 72-hour controlled diet

- Focused physical exam to evaluate gastrointestinal tract, heart, and lungs
- Record body height and weight
- Record vital signs while sitting (blood pressure, pulse rate, breathing rate, and temperature)
- Record any changes in AEs and concomitant medication
- Instruct/dispense study drug for confinement period
- Assess and record malabsorption signs and symptoms
- Marker-to-marker stool collection and stool weight (central laboratory will weigh the stool that is collected)
- Collect urine sample for urinalysis
- Perform a urine pregnancy test (urine dip stick), if applicable
- Collect samples for hematology, clinical chemistry, PT/INR, and aPTT
- Collect samples for fasting lipids after patients have been in a fasting status for at least 8 hours (insulin dependent diabetics may be excluded from fasting).
- Record all fat, protein, and dose of study drug taken with every meal and snack during the confinement period
- Verify study drug count on the last day of confinement
- Return adrulipase on the last day of confinement

At the end of the supervised confinement (once the second blue dye marker sample has been collected), patients will return to their prestudy porcine PERT dose.

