5.2. Per-Protocol Population

The per-protocol (PP) population is a subset of the mITT population and includes all mITT subjects without major protocol deviations that could impact the efficacy analyses. Protocol deviations will be captured throughout the study and classified as minor or major prior to database lock. Each major deviation will be categorized as either important or not important with respect to the effect on the primary endpoint analysis.

Subjects who are found to be <80% compliant with adrilipase will also be excluded from the PP population. The PP population will be used as supportive to the mITT population.

Prior to database lock, the protocol deviations will be reviewed and the PP Population will be determined.

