8.2. Extent of Exposure

The following summaries will be displayed overall and by maximum dose of adrulipase received during the study.

Time on treatment (days) will be calculated as: date of last dose of study drug – date first dose of study drug + 1. Time on treatment will be summarized using descriptive statistics for subjects in the safety population. Time on treatment will also be displayed separately for each dose (e.g. time on low dose [1.2 g/day], time on medium dose [1.95 g/day], time on high dose [2.4 g/day]).

For each dose, whether the subject started dosing at that dose level, reason for dose increase (for doses after initial dose), and date/time of first and last dose at that dose level will be listed for all subjects in the safety population.

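### SAP 7.3 adds a whole day to an elapsed date/time count, so a fully adherent Part 1 patient scores about 94–98% and the 80% Per-Protocol cut acts at about 82–85%

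*SAP*

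**What the plan says.** SAP 7.3: "Treatment compliance will be summarized in terms of g/day using a compliance rate". The rate is actual g/day over expected g/day. Actual g/day is capsules dispensed minus capsules returned, times 0.15 g, divided by days on adrulipase. Those days are the date/time of last dose minus the "date/time of first adrulipase dose}) / 86400 + 1".

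On the other half of the ratio, "The expected dose for adrulipase depends on whether the subject titrated to a higher dose during the study". The printed expression divides 1.2 g by days on low dose, divides 1.95 g by days on medium dose, multiplies 2.4 g by days on high dose, and adds the three.

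The result drives a fixed rule: "subjects found to be <80% compliant with adrulipase will be excluded from the PP population". SAP 5.2 repeats that such patients "will also be excluded from the PP population".

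For exposure, SAP 8.2 counts days from dates only: "date of last dose of study drug – date first dose of study drug + 1".

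**The concern.** Dividing seconds by 86400 gives elapsed days as a fraction. Adding 1 is right when whole dates are subtracted, because it restores the first calendar day. It is wrong for clock time: doses from first to last cover the elapsed time plus roughly one between-meal interval, not plus a full day. The denominator is therefore too long and actual g/day too low.

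The low score matters because the 80% cut is automatic. A patient whose true adherence is just above 80% would drop out of the Per-Protocol summaries of CFA (SAP 9.2.3) and CNA (SAP 9.3.3). With about 12 patients, losing one visibly changes a summary. SAP 7.3 and 8.2 also give different days on drug for the same patient.

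**Working it through.** **Inputs from the documents.** Capsules of 0.15 g at 8, 13, 16 or 22 per day over five eating occasions (protocol 8.4.1, Table 3). These reproduce the stated doses: 8 × 0.15 = 1.2, 13 × 0.15 = 1.95, 16 × 0.15 = 2.4 and 22 × 0.15 = 3.3 g/day. Protocol 9.2.4.1 requires at least 16 (Part 1) or 10 (Part 2) days of dosing before confinement. The controlled diet lasts 3 days, so courses last about 19 or 13 days at least. The nominal treatment periods are about 21 and 14 days. The clock times of the first and last dose are not fixed: the first follows Visit 3, and adrulipase stops once the second marker stool is collected.

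**Assumptions.** Meals and snacks at 08:00, 10:30, 13:00, 15:30 and 18:00; every scheduled capsule taken; expected dose equal to the planned g/day.

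**Step 1: overcount.** Dose-days = capsules taken ÷ capsules per day. Overcount = SAP 7.3 days − dose-days.

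- Case A, 1.2 g/day, breakfast Day 1 to dinner Day 21: 21 × 8 = 168 capsules = 21 dose-days. Elapsed 20 + 10/24 = 20.417; SAP 7.3 days 21.417; overcount 0.42. Score: 168 × 0.15 / 21.417 = 1.177 g/day; 1.177/1.2 = 98.1%.
- Case B, 1.2 g/day, dinner Day 1 to breakfast Day 21: 2 + 19 × 8 + 2 = 156 capsules = 19.5 dose-days. Elapsed 20 − 10/24 = 19.583; SAP 7.3 days 20.583; overcount 1.08. Score: 156 × 0.15 / 20.583 = 1.137 g/day; 1.137/1.2 = 94.7%.

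Over all 25 pairs of first and last eating occasion and all four regimens, the overcount is 0.42 to 1.12 days and always positive.

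**Step 2: scores and effective cut.** For given first and last dose times the score is proportional to capsules taken, so the effective cut = 80% ÷ (score at full adherence).

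| Regimen | Calendar days | Score at full adherence | Effective cut |
|---|---|---|---|
| Part 1, 1.2 g/day | 19 | 94.2–97.9% | 81.8–85.0% |
| Part 1, 1.2 g/day | 21 | 94.7–98.1% | 81.6–84.4% |
| Part 2, 3.3 g/day | 13 | 91.7–96.9% | 82.6–87.3% |
| Part 2, 3.3 g/day | 14 | 92.3–97.1% | 82.4–86.7% |

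The lowest value for any Part 1 regimen is 94.0% (1.95 g/day, 19 days; cut 85.1%). With alternative times of 07:00, 10:00, 12:00, 15:00 and 21:00, the scores are 95.0–97.3% (1.2 g/day, 21 days) and 92.3–96.0% (3.3 g/day, 14 days).

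**Step 3: the expected dose as printed.** In Case A the printed expression gives 1.2/21 = 0.0571 (other terms taken as zero), so the score is 1.177/0.0571, about 2059%. Now take 5, 5 and 11 days on low, medium and high dose, breakfast to dinner. Total = 6 + 9.75 + 26.4 = 42.15 g; actual = 42.15/21.417 = 1.968 g/day; printed expected dose = 1.2/5 + 1.95/5 + 2.4 × 11 = 27.03; score 7.3%. Against the planned mean, 42.15/21 = 2.007 g/day, the score is 98.1%. If the expected 42.15 g were divided by the same 21.417 days, the overcount would cancel and the score would be 100%.

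**Step 4: the two obvious repairs.**

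| | SAP 7.3 | +1 deleted | SAP 8.2 date count |
|---|---|---|---|
| Case A | 98.1% | 168 × 0.15 / 20.417 / 1.2 = 102.9% | 168 × 0.15 / 21 / 1.2 = 100% |
| Case B | 94.7% | 156 × 0.15 / 19.583 / 1.2 = 99.6% | 156 × 0.15 / 21 / 1.2 = 92.9% |

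Deleting +1 leaves a smaller error, which can go either way. The date count is exact only when the first and last days are full dosing days; otherwise it can score lower than the present formula.

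**The case against.** **The percentages are not what the printed rule yields.** This is correct. As printed, the rule gives figures such as 2059% or 7.3%, and under one natural repair the overcount cancels. The figures here are conditional on expected dose meaning planned g/day. That is the natural reading, since SAP 7.3 labels the quantity in g/day, but it is a reading. A reader might infer that every patient is scored low however the expression is repaired; the documents do not support that.

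**The larger figures belong to Part 2.** SAP section 2 states that it was written to protocol Version 1.0, and it names only the three Part 1 doses. A reader might take 92% and 87% as this SAP's range. They arise only if the rule is carried over to the shorter course. Protocol 11.7.1 does send both parts to the SAP for analysis, so the carry-over is worth anticipating.

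**Meal times are assumed.** This stands for the exact size, not the direction: the overcount was positive for every pair under both sets of times.

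**Visit 6 capsules.** SAP 7.3 has a note beginning "Note that since capsules are dispensed at one visit and returned at one visit", while protocol 9.2.3 lists "Instruct/dispense study drug for confinement period" at Visit 6. A reader might infer that confinement capsules go uncounted. If four days' worth did, a perfectly adherent patient would score 9/13 = 69% or 15/19 = 79%. The documents do not support this. The formula's dispensed count has no visit limit, the rest of the note is not legible in the available text, and similar dispensing wording appears at Visit 2, when patients are still on PERT. The two texts need one clarifying line, nothing more.

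**The consequence is small.** This is agreed. The Per-Protocol population is supportive, all efficacy summaries are descriptive, and no test depends on the cut.

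**Conclusion.** The day count in SAP 7.3 is wrong for date/time data and should be corrected, together with the larger expected-dose error in the same section. With expected dose read as planned g/day and meal times assumed, full adherence in Part 1 (about 19–21 days) scores about 94–98%, and the 80% cut acts at about 82–85%. Carried over to Part 2 (about 13–14 days), the figures would be about 92–97% and 82–87%. Only a patient with true adherence between 80% and the effective cut would be wrongly excluded, and nothing in the documents says one is expected. The effect stops at the supportive Per-Protocol summaries of CFA and CNA. It would be wrong to infer any effect on the primary mITT analysis.

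**What to change.** In SAP 7.3, replace the g/day ratio with:

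compliance (%) = 100 × (all capsules dispensed − capsules returned) ÷ (capsules scheduled for the eating occasions from first to last dose, at the dose level then assigned).

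Take the scheduled capsules from protocol Table 3, counting only the occasions that fall within partial first and last days. Where a patient has an agreed different split, use that split on those days. A fully adherent patient then scores 100% and the cut is a true 80%. Neither the day count nor the expected-dose expression is needed any longer.

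Do not simply delete the +1 or borrow the SAP 8.2 date count for compliance; Step 4 shows that neither is exact. Keep the 8.2 count for exposure only. State that dispensed capsules include any issued at Visit 6. If the SAP is extended to Part 2, the same definition applies unchanged.

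The cost is a few lines of SAP text and one derivation, settled before the Per-Protocol population is fixed at database lock. Capsule counts and the date/times of first and last dose at each level are already due to be listed (SAP 7.3 and 8.2), so no new data are needed.

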	Consent and Initial Evaluations	CFA on PERT	Dispense	Optimize	Optimize	CFA on Adrulipase	STUDY/EARLY TERMINATION
Visit Number	1 ^a	2 ^b	3	4 (T) ^c	5 (T) ^c	6 ^b	7
Study Week	-6	-2	1	2	3	4	5
Study Days	-42	-14	1	5	10	16	28
Visit Window (days)	+7	±7	±2	±2	±2	+5	±7
Switch back to Prescribed Porcine PERT							
Switch back to prescribed porcine PERT ^k						X	X

a Screening procedures can occur up to 14 days before the first day of supervised confinement (V2). As some lab assessments require fasting status, site may utilize a pre-screening telephone consent process to obtain agreement in advance for patients to adhere fasting for at least 8 hours. Patients will also be asked to bring a stool sample to V1

b Visit 2 and Visit 6 are the first and second scheduled confinement visits and can take up to 7 days. A 5-day window is permitted around the scheduled confinement for both V2 and V6 to accommodate for scheduling. Dosing must have occurred for at least 16 days prior to the start of the scheduled confinement.

c Visits 4 and 5 are telephone visits to assess any changes to AEs and concomitant medications in addition to confirming the visit date for the next scheduled supervised confinement.

d The Focused Physical Exam will evaluate gastrointestinal tract, heart, and lungs.

e At the end of V6 (after the last stool sample has been collected), Patients will begin treatment with their prestudy porcine PERT.

f The stool samples will be sent to the central laboratory and CFA, CNA, and stool weight will be measured.

g A serum pregnancy test must be conducted in females of reproductive potential at screening Visit 1. Pregnancy status will be re-evaluated via urine pregnancy test in these Patients at Visit 3, 6 and at the End-of-Study or Early Termination visit (Visit 7).

h On the basis of laboratory safety values, unscheduled hepatic monitoring testing may be performed in patients with new, clinically meaningful increases in liver function tests occurring during the study, in consultation with study designated Medical Monitor. These tests are to be done through the central labs.

i Fasting labs should be taken after patients have been in a fasting status for at least 8 hours at Visits 1 and 6.

j Fecal pancreatic elastase will be collected at Visit 1 and sent for analysis to the central laboratory.

k At the end of the supervised confinement (once the second blue dye marker sample has been collected), patients will return to their prestudy porcine PERT dose.

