3.2. Overall Study Design and Plan

This is a Phase 2, single arm pilot study assessing the safety and efficacy of adrulipase in an enteric microgranule formulation. Patients with a confirmed diagnosis of cystic fibrosis who are 18 years of age or greater will be screened for eligibility if they have been clinically controlled on a stable dose of commercial pancreatic enzyme replacement therapy (PERT) for at least one month. Patients on cystic fibrosis transmembrane conductance regulator (CFTR) modulator therapies must have been on a stable dose for at least 3 months prior to study entry, and no dose changes will be made during the study. Patients receiving gastric acid suppressants must have been on a stable dose for at least one month prior to study entry and no dose changes will be made during the study. Upon obtaining an informed consent, potentially eligible patients will receive dietary counselling during the week prior to the scheduled date of confinement for collecting stool samples for calculation of baseline coefficient of fat absorption (CFA). This counselling will emphasize the importance of dietary stability during the study. Patients found to have a CFA of 80% or greater while receiving their commercial PERT and meeting the other eligibility criteria will be enrolled into the study.

Upon study enrolment, the patient will be switched from their commercial PERT to receive adrulipase. The patient will remain on study for approximately three weeks, after which a repeat CFA will be obtained. A dose titration scheme will be used for determining whether a low, medium, or high dose of adrulipase may succeed in controlling signs and symptoms of exocrine pancreatic insufficiency (EPI) and provide a CFA of 80% or greater. Patients will initially receive a low dose of adrulipase. Upon the appearance of EPI symptoms, lasting at least three days, and upon discussion with the investigator, the patient will be switched to the medium dose of adrulipase. If signs and symptoms of EPI persist for three or more days, the patient will be switched to the high dose of adrulipase. After patients reach 3 weeks of study and complete their end of study CFA, they will be returned to their pre-study commercial PERT. An end of study safety visit will be scheduled for one week after finishing adrulipase therapy.

Safety assessments will be made by collecting adverse events, safety lab assessments, and immunologic assays to assess drug induced immune responses.

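### No reading of the SAP's expected-dose formula gives a generally valid g/day figure, so the 80% compliance rule, if programmed literally, would misclassify patients for the Per-Protocol set

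*SAP*

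**What the plan says.** SAP 7.3 states that "Treatment compliance will be summarized in terms of g/day using a compliance rate", and defines the rate as 100 times actual g/day over expected g/day. The actual dose is soundly built: capsules dispensed minus capsules returned, times 0.15 g, divided by days on adrulipase.

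For the denominator, "The expected dose for adrulipase depends on whether the subject titrated to a higher dose during the study". The expression printed next has three terms. The first is 1.2 g with a slash before days on low dose. The second is 1.95 g with a slash before days on medium dose. The third is 2.4 g beside days on high dose with no operator. Nothing is divided by total days.

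The consequence is mandatory: "subjects found to be <80% compliant with adrulipase will be excluded from the PP population". SAP 5.2 repeats the rule and describes the Per-Protocol (PP) set as supportive to the mITT population. PP summaries of CFA and CNA are planned in SAP 9.2.3 and 9.3.3.

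**The concern.** Both halves of the ratio must be in g/day. The titration wording points to a time-weighted prescribed dose, but the printed expression does not compute one. The score decides PP membership without further judgement, so a wrong denominator can remove adherent patients or keep non-adherent ones, depending on how a programmer reads the line.

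Most of Part 1 reaches the term whose operator is unclear. Protocol 6.7 reports that five of the six patients enrolled when version 2.0 was written had been dosed at 2.4 g/day. In a study of approximately 12 patients, a few wrong inclusions or exclusions can change a PP summary noticeably.

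**Working it through.** **Dose levels.** Protocol 8.4.1 gives 8, 13 and 16 capsules a day in Part 1. At 0.15 g each this is 1.2, 1.95 and 2.4 g/day, so the dose constants are right. The fault lies in how they are combined.

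**Target.** With L, M and H days on low, medium and high, the prescribed mean daily dose is (1.2L + 1.95M + 2.4H)/(L + M + H).

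**Assumptions.** The documents do not give days per level. I took whole days, 21 in total, full adherence, at least 3 days on low and on medium, and at least 1 on high. The 3-day minimum comes from the titration rule in SAP 3.2: "Upon the appearance of EPI symptoms, lasting at least three days, and upon discussion with the investigator" for the first step and "If signs and symptoms of EPI persist for three or more days, the patient will be switched to the high dose" for the second. The number of low-medium-high splits is C(16,2) = 120.

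**Worked example, 5/5/11 days.** Actual dose = (6.00 + 9.75 + 26.40)/21 = 42.15/21 = 2.007 g/day.

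- As printed: 1.2/5 + 1.95/5 + 2.4 × 11 = 27.03
- All divide: 1.2/5 + 1.95/5 + 2.4/11 = 0.848
- All multiply: 42.15 (total grams, not g/day)
- Divisors as unit labels, rates summed: 1.2 + 1.95 + 2.4 = 5.55

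| Reading | 5/5/11 score | Range over 120 splits | Fully adherent splits below 80% |
|---|---|---|---|
| As printed | 7.4% | 5.8% (3/3/15) to 64.8% (4/16/1) | 120 |
| All divide | 236.6% | 43.7% (17/3/1) to 250% (5/7/9) | 16 |
| All multiply | 4.8% (1/21) | 4.8% | 120 |
| Unit label | 36.2% | 24.6% (17/3/1) to 39.0% (3/3/15) | 120 |

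**Wrong retention.** If all terms divide, 99 of the 120 splits score above 100% at full adherence. At 50% adherence 70 of 120 still pass; at 40%, 46 do. A 5/5/11 patient passes on 0.8 × 0.848/2.007 = 33.8% of capsules.

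**Patients who stop earlier.** As printed, a 7/14/0 patient has expected dose 1.2/7 + 1.95/14 = 0.311 against an actual 35.7/21 = 1.700. That scores 547%, and the patient would pass on 0.8 × 0.3107/1.700 = 14.6% of capsules. A low-only patient gives 1.95/0, which is undefined; if all terms divide, so is anyone who never reaches high (2.4/0). The SAP has no rule for zero days. Under the unit-label reading, a low-only patient has expected dose 1.2 and scores a correct 100%.

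**Sensitivity to duration.** The protocol's Part 1 schedule says: "Dosing must have occurred for at least 16 days prior to the start of the scheduled confinement". Adding the 72-hour collection gives about 19 days on the normal schedule. The upper end is 16 + 5 (visit window) + 7 (longest confinement) = 28 days. Over 19 to 28 days the three-level ranges are 4.1% to 67.1% as printed, 42.7% to 333% if all divide, and 3.6% (1/28) to 5.3% (1/19) if all multiply. Protocol 8.1 allows earlier confinement in special circumstances; starting the range at 16 days changes only the last figure, to 6.3% (1/16). Dropping the 3-day minimum at 21 days (190 splits) leaves the as-printed maximum at 64.8%.

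**The case against.** **The text came from a PDF.** The missing operator in the third term may be an extraction artefact. That stands. A reader might infer that the five patients dosed at 2.4 g/day will all be dropped from PP. The documents do not support this: it depends on that one character, and those patients' day splits are not given. Restoring the slash, however, does not repair the formula.

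**The correction may be in text we cannot see.** Section 7.3 ends with a note that breaks off. Its visible part begins "Note that since capsules are dispensed at one visit and returned at one visit" and concerns capsule counts, not expected dose. The rest cannot be assessed, so the statement that nothing corrects the formula covers visible text only.

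**One reading is right for some patients.** This also stands. A reader might infer that the formula never returns the prescribed dose. The unit-label reading does so for low-only patients, and all-divide comes within 95% to 105% in 3 of the 120 splits by coincidence. Neither works across titration paths.

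**A restored slash would not let most poor adherers through.** Whether it does depends on what counts as poor: 70 of 120 splits pass at 50% adherence but only 46 at 40%. Split counts are not patient frequencies either, so no general statement about most patients is justified.

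**Someone will notice.** Scores such as 7% or 547% would stand out in the compliance listing, and the PP set is settled before database lock. This makes silent error less likely. But SAP section 2 gives the SAP precedence over the protocol, and two programmers could repair the line differently. An unrecorded repair to a prespecified exclusion rule is poor practice.

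**Conclusion.** The point holds. The expression lacks division by total days, and no reading of it is generally valid in g/day. If it is programmed literally, PP membership will be wrong, and who is misclassified depends on the reading. As printed, all-multiply and unit-label each exclude all 120 fully adherent three-level splits. All-divide excludes 16 and can keep patients with low adherence. These counts rest on the assumed 21 whole days and 3-day minimums, but the as-printed result does not depend on them: no three-level split reaches 80% from 16 to 28 days, or at 21 days without the minimum.

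The reach is small. It covers the compliance summary and listing and the supportive, descriptive PP summaries of CFA and CNA. A reader might infer that the main efficacy result is compromised. It is not: the primary summary uses mITT (SAP 9.2.2). The count of patients with CFA of at least 80%, its best-case and worst-case repeats (SAP 9.2.4) and the safety summaries do not use the compliance score. It should be corrected, but it does not threaten the study's conclusions.

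**What to change.** Replace the expression in SAP 7.3 with:

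Expected dose (g/day) = [1.2 × days low + 1.95 × days medium + 2.4 × days high] / (days low + days medium + days high)

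State three conventions with it:

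- Unused levels contribute zero.
- Each calendar day, including a switch day, belongs to exactly one level, so that level days sum to total days on adrulipase.
- The actual-dose formula uses the same total-day denominator. SAP 8.2 already defines a whole-day count (last dose date minus first dose date plus 1) that would serve.

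Full adherence then scores 100% on every path; 5/5/11 gives 2.007/2.007.

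The date/time-plus-1 count now in SAP 7.3 must not be applied separately to each level. Suppose dosing runs from 08:00 on the first day to 18:00 on the last day at each level. Each level then gains 10/24 = 0.417 day, the expected grams become 42.15 + 0.417 × 5.55 = 44.46, and an adherent 5/5/11 patient scores 42.15/44.46 = 94.8%. That is harmless at an 80% cut but avoidable.

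Separately, the SAP was written from protocol version 1.0. When it is updated, the dose level that Protocol 8.4.2 already assigns to Part 2 (3.3 g/day) should enter the same formula.

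The cost is one SAP line with its conventions and the matching derivation in the compliance dataset specification, made before the PP set is determined. No new data are needed.
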